5.5. Supportive Care Guidelines

- Medications may be administered for the management of symptoms associated with the administration of FF-10501-01, as required.
- Prophylactic pre-medication will not be used routinely. Adequate treatment for nausea and/or vomiting and diarrhea is permitted during Cycle 1. After Cycle 1, prophylaxis of nausea and/or vomiting and diarrhea is permitted.
- Granulocyte stimulating growth factors (e.g., G-CSF or GM-CSF) are not allowed during Cycle 1 except for the following situations (defined as DLTs): Grade 4 neutropenia lasting 7 days or more, or failure of the absolute neutrophil count (ANC) to recover to Grade 1 within 12 weeks. After Cycle 1, use of granulocyte growth factors are allowed for prophylaxis or management of neutropenia.
- Erythropoiesis-stimulating agents, transfusions, etc. are permitted for management of hematologic toxicities.

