7.2.2.2. Subjects with MDS or CMML

- **Complete Remission (CR)**

The subject must be free of all symptoms related to leukemia and have an absolute neutrophil count $\geq 1.0 \times 10^9/L$, platelet count $\geq 100 \times 10^9/L$, bone marrow $\leq 5\%$ myeloblasts, with normal maturation of all cell lines, hemoglobin $\geq 11\text{g/dL}$, and no blasts in the peripheral blood

- **Partial Remission (PR)**

All CR criteria with $\geq 50\%$ decrease in bone marrow blasts over pre-treatment (but still $> 5\%$)

- **Marrow CR**
In bone marrow, $\leq 5\%$ myeloblasts and decrease by $\geq 50\%$ over pre-treatment
- **Hematologic Improvement (HI) (subjects with MDS only)**
 - **Erythroid Response (HI-E)**
 - **Major Response**
 - ◊ For subjects with pretreatment hemoglobin $< 11 \text{ g/dL}$, $> 2 \text{ g/dL}$ increase in hemoglobin
 - ◊ For RBC transfusion-dependent subjects, transfusion independence
 - **Minor Response**
 - ◊ For subjects with pretreatment hemoglobin $< 11 \text{ g/dL}$, 1 to 2 g/dL increase in hemoglobin
 - ◊ For RBC transfusion-dependent subjects, $\geq 50\%$ decrease in transfusion requirements
 - **Platelet Response (HI-P)**
 - **Major Response**
 - ◊ For subjects with a pretreatment platelet count $< 100 \times 10^9/\text{L}$, an absolute increase of $\geq 30 \times 10^9/\text{L}$
 - ◊ For platelet transfusion-dependent subjects, stabilization of platelet transfusion independence
 - **Minor Response**
 - ◊ For subjects with a pretreatment platelet count $< 100 \times 10^9/\text{L}$, a $\geq 50\%$ increase in platelet count with a net increase $> 10 \times 10^9/\text{L}$ but $< 30 \times 10^9/\text{L}$
 - **Neutrophil Response (HI-N)**
 - **Major Response**
 - ◊ For absolute neutrophil count (ANC) $< 1.5 \times 10^9/\text{L}$ before therapy, $\geq 100\%$ increase or an absolute increase of $\geq 0.5 \times 10^9/\text{L}$, whichever is greater
 - **Minor Response**

- ◊ For ANC $< 1.5 \times 10^9/L$ before therapy, ANC $\geq 100\%$, but absolute increase $< 0.5 \times 10^9/L$

- **Progressive Disease**

Subject did not achieve PR, CR or marrow CR or is otherwise a non-responder.

- **Relapse after CR or PR**

One or more of the following:

- Return to pretreatment bone marrow blast percentage
- Decrement of $\geq 50\%$ from maximum remission/response levels in granulocytes or platelets
- Reduction in hemoglobin concentration by ≥ 2 g/dL or transfusion dependence.

- **Progression or Relapse after Hematologic Improvement**

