One or more of the following:

- A $\geq 50\%$ decrement from maximum response levels in granulocytes or platelets
- A reduction in hemoglobin concentration by ≥ 2 g/dL
- Transfusion

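### Bare transfusion item in the criteria for progression after hematologic improvement conflicts with the rest of Section 7.2.2.2 and could create PFS events from supportive care

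*Protocol*

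**What the plan says.** The last list in Protocol Section 7.2.2.2 is headed "Progression or Relapse after Hematologic Improvement". It is introduced by "One or more of the following", so any single item is enough. The items are:

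- a fall of at least 50% from maximum response in granulocytes or platelets;
- "A reduction in hemoglobin concentration by" at least 2 g/dL;
- the one word transfusion, without qualification.

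The list just above it, for relapse after CR or PR, ends its hemoglobin item with "g/dL or transfusion dependence".

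HI is restricted to "subjects with MDS only". Among its categories, a transfusion-dependent subject is a major erythroid responder on becoming independent of transfusion, and a minor responder with at least a 50% "decrease in transfusion requirements".

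Section 5.5 states: "Erythropoiesis-stimulating agents, transfusions, etc. are permitted for management of hematologic toxicities".

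PFS is a secondary endpoint. Protocol Sections 7.2.3.2 and 8.3.2.2 and SAP Section 3.3.2 count the first objective evidence of progression, or death, and name no criteria list. SAP Section 4.3 includes a blood transfusion listing, but nothing ties it to the PFS derivation.

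**The concern.** Read literally, one transfusion of any product for any reason is progression in a subject with HI. Transfusion is permitted supportive care, and the trial population is prone to cytopenia. In the completed Japanese MDS study (Protocol Section 1.7.1), anemia and decreased platelet count were each reported in 3 of 9 subjects, regardless of cause. Because no cell type is stated, a platelet transfusion in an erythroid responder would also qualify.

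If these events enter PFS, the endpoint would partly measure toxicity and local transfusion practice rather than disease. PFS is estimated in small groups: Phase 1 by dose cohort, and Phase 2a by disease cohort among 20 planned MDS/CMML subjects. A few misclassified events could therefore matter. The definition of progression also bears on treatment, since Section 5.3 continues treatment until progression is confirmed.

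**Working it through.** The documents give no PFS event count, power or transfusion rate, so there is no figure to reproduce. The check is a comparison of text, followed by an illustration on assumed rates.

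**1. Against the parallel list.** Relapse after CR or PR requires "or transfusion dependence"; relapse after HI requires only a transfusion. A subject with CR or PR who also meets an HI criterion falls under both lists. One isolated transfusion is then an event under one list and not under the other.

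**2. Against the response definition.** For a transfusion-dependent subject, independence is a major erythroid response. A subject who is only a minor responder on that criterion is therefore still being transfused. The next transfusion meets the progression item, so a category of improvement turns into progression without any worsening. This is the clearest sign that the bare word cannot work as written.

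**3. Against supportive care.** Section 5.5 permits transfusion for hematologic toxicity. Section 7.2.2.2 has no exclusion by cause in the HI list. By contrast, AML recurrence in Section 7.2.2.1 does exclude marrow blasts that the investigator attributes to another cause.

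**4. In which subjects the item could decide PFS.** This depends on which list is used.

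| Subject with MDS | Lists that apply on a literal reading | Role of the transfusion item |
|---|---|---|
| HI only | Progressive Disease (no PR, CR or marrow CR) and the HI list | Already progressive under the first; the item decides only if that definition is set aside |
| CR or PR, plus HI | Relapse after CR/PR and the HI list | The two lists disagree on an isolated transfusion |
| Marrow CR plus HI | HI list only: Progressive Disease excludes marrow CR on its first limb, and the relapse list names only CR and PR | The item can decide the event alone |

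**5. Illustration, assumed rates only.** Let *q* be the assumed probability per cycle of at least one transfusion unrelated to progression, constant and independent across cycles. The chance of meeting the item within *k* cycles after HI is 1 − (1 − *q*)^*k*. The median number of cycles to the event, if this were the only risk, is ln 0.5 / ln(1 − *q*).

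| *q* (assumed) | 3 cycles | 5 cycles | Median, cycles |
|---|---|---|---|
| 0.05 | 1 − 0.95³ = 14% | 1 − 0.95⁵ = 23% | 13.5 |
| 0.10 | 1 − 0.90³ = 27% | 1 − 0.90⁵ = 41% | 6.6 |
| 0.20 | 1 − 0.80³ = 49% | 1 − 0.80⁵ = 67% | 3.1 |
| 0.30 | 1 − 0.70³ = 66% | 1 − 0.70⁵ = 83% | 1.9 |

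The table shows how sensitive the rule is to transfusion frequency. It does not estimate the effect in this trial.

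**The case against.** **A word may be missing.** A one-word item whose counterpart is a two-word phrase looks like a dropped word, in the protocol or in the text extraction. The documents cannot settle this. If the source has the word, the sponsor need only confirm it, and the conflicts over transfusion dependence and isolated supportive transfusions ease. In the text as given, they remain.

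**The link to PFS is inferred.** No PFS definition cites the HI list, and the literal Progressive Disease definition already captures HI-only subjects. A reader might infer that every responding subject who is transfused becomes a PFS event. The documents do not support that: the case is firmest for the narrower group with marrow CR plus HI. The broader defect is that PFS has no single stated progression definition. Correcting Progressive Disease alone would still leave the transfusion item in place.

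**Correcting one item is not a complete cure.** The neighbouring items on counts and hemoglobin also carry no toxicity exclusion, so a drug-related cytopenia could trip one of them anyway. Transfusion dependence is itself undefined. Both points stand and limit what the change achieves.

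**Size.** A reader might take a subject stable for 6 cycles (6 × 28 = 168 days) and transfused in Cycle 3, with an event by Day 84 (3 × 28), and conclude that PFS is halved. That example is assumed. A subject still stable at Day 168 has not progressed, so 168 is a lower bound rather than a true time. The end of Cycle 6 is not a scheduled assessment, and an HI-only subject could already count as progressive at the end of Cycle 1.

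**Other readings that go too far.** Section 5.5 names hematologic toxicity, not bleeding. Section 5.3 requires confirmation of progression, so it does not follow that one transfusion ends treatment.

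**Conclusion.** The conflict is real on the text as given. A bare transfusion item is enough for progression or relapse after HI, and it contradicts the parallel relapse list and the minor erythroid response; nor does it allow for the supportive care permitted in Section 5.5.

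The consequence for PFS is conditional on this list supplying progression events. If it does, an MDS subject with HI could be scored as progressed after a single supportive transfusion. The reach is limited: HI applies to MDS only, PFS is a descriptive secondary endpoint with no hypothesis test planned (SAP Section 2.4.2), and neither objective response nor the blast-count endpoint is affected. Protocol Section 1.7.2 reports 8 MDS patients treated and one platelet response. No size can be put on the bias, because the documents give no transfusion rate. The item should be corrected, in proportion to that reach.

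**What to change.** 1. **Protocol Section 7.2.2.2.** For the PFS endpoint, make the transfusion item after HI consistent with transfusion dependence in the list above it, or confirm that a word was dropped. State what dependence means for the endpoint, since neither document defines it.
2. **SAP Section 3.3.2.** State which criteria list defines the PFS progression event for MDS subjects, and that an isolated transfusion is not by itself an event. Reconcile this with the Progressive Disease definition, and say how the neighbouring count and hemoglobin items are read when drug toxicity explains the change.
3. **Review of data.** Use the blood transfusion listing already planned in SAP Section 4.3 to check subjects with HI.
4. **Reconciliation.** Because treatment continues until confirmed progression, the sponsor must reconcile Sections 5.3, 5.5 and 7.2.2.2. The changes above concern the endpoint only; no treatment-stopping rule is proposed.

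The cost is one protocol item with its definition and a few sentences in the SAP. No new data collection is needed for the review, since a transfusion listing is already planned.

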7.2.3. Efficacy Endpoints

7.2.3.1. Primary Efficacy Endpoint

To evaluate the proportion of subjects with objective response achieved within 3 cycles of treatment with FF-10501-01 (i.e., within 3 months) in subjects with relapsed/refractory AML or relapsed/refractory high-risk MDS or CMML.

- **Subjects with AML**

Objective responses for subjects with AML include complete remission (CR), complete remission with incomplete blood count recovery (CRi) and partial remission (PR) as defined above.

- **Subjects with MDS**

Objective responses for subjects with high-risk MDS include complete remission (CR), partial remission (PR), and marrow CR as defined above.

- **Subjects with CMML**

Objective responses for subjects with CMML include complete remission (CR), partial remission (PR) and marrow CR as defined above.

7.2.3.2. Secondary Efficacy Endpoints

The proportion of subjects with MDS who have hematologic improvement in peripheral blood or bone marrow blast count at any time after initiation of treatment with FF-10501-

01. Hematologic improvement in blast count is defined as $\geq 50\%$ reduction in peripheral blood or bone marrow blast count when compared with the baseline value.

Progression-Free Survival: length of time from the date of first administration of study drug to the first objective evidence of disease progression or death, whichever is earlier.

Overall Survival: length of time from the date of first administration of study drug to the date of death from any cause

7.2.4. Timing of Assessments to Determine Response

Disease assessments will be made at the end of Cycle 1 and Cycle 3 and every two cycles thereafter. Disease assessments may be made at other time points at the discretion of the Investigator.

7.2.5. Pharmacokinetic Endpoints

Mean plasma concentrations of FF-10501 will be determined at each time point. Because plasma concentrations will be determined at a limited number of time points during the study, a complete pharmacokinetic profile of FF-10501-01 at each dose level will not be possible. Limited pharmacokinetic analyses will be performed.

7.2.6. Pharmacodynamic (PD) Endpoint

XMP is an intermediate in purine metabolism. It is formed from inosine monophosphate via the action of IMPDH, and is converted to guanosine monophosphate (GMP) via the action of GMP synthase (see **Figure 1**). The mechanism of action of FF-10501-01, namely, inhibition of IMPDH, should be associated with a decrease in XMP. Therefore, as a measure of pharmacologic activity of FF-10501-01 and preliminary measure of efficacy, levels of XMP in peripheral blood cells will be assessed in this study.

8. STATISTICAL METHODOLOGY

8.1. Determination of Sample Size

Phase 1: The sample size reflects requirements associated with a 3+3 design. A total of 3 to 36 subjects are planned (3 to 6 subjects in each of 6 dose cohorts).

Phase 2: The sample size reflects an additional 20 MDS/CMMI patients to be treated at the MTD.

8.2. Analysis Populations

The full analysis set (FAS) includes all subjects who are administered any fraction of a dose of study medication. For a particular measure, the per-protocol set (PPS) includes those subjects in the FAS who have a valid baseline and one or more post-treatment assessments for that measure of interest.

The FF-10501-01 PK population consists of all subjects in the FAS who complete all PK assessments.

The FF-10501-01 PD population consists of all subjects in the FAS who complete all PD assessments.

8.3. Statistical Analysis Methods

All data will be analyzed using Statistical Analysis System (SAS Version 9.3 or higher for Windows, SAS Institute, Cary, NC). Continuous variables will be summarized using number, mean, standard deviation, median, minimum, and maximum. Categorical variables will be summarized using number and frequencies.

8.3.1. Safety Analyses

8.3.1.1. Adverse Events

All safety endpoints will be summarized using descriptive statistics and will be based on the FAS dataset.

All AEs will be coded based on the Medical Dictionary for Regulatory Affairs (MedDRA; Version 15.0 or higher). An AE will be considered a treatment emergent adverse event (TEAE) if the onset is after the first dose of study drug or if the condition was present at baseline but worsened after the first dose.

All AEs for each subject will be listed, including intensity grading, relationship to study drug, action taken and outcome. Subject listings of deaths, SAEs, and AEs leading to treatment discontinuation will be provided. Subject narratives will be provided for deaths, SAEs and other significant AEs. Summary tables will be prepared to examine TEAE severity and relationship to study treatment.

AE summaries will be produced separately for each dose cohort and overall, and each disease cohort by dose and overall. All summaries will show, by subject group, dose cohort and overall, the number and percentage of subjects experiencing at least 1 TEAE of each preferred term, arranged by system organ class, and the number of occurrences of the event. Separate summaries will be produced by relationship to study medication, by severity, and for those events with an incidence rate of at least 2% in any group or overall.

SAEs will be summarized in a similar manner; overall, by relationship to study medication, and by severity.

In addition to the above, summaries of the number and percentage of subjects discontinuing the study due to AEs and, due to death, will be presented.

8.3.1.2. Laboratory Data

Laboratory data will be listed by subject. Values above and below normal ranges will be indicated, and whether statistically significant. All laboratory values will be graded according to the NCI-CTCAE version 4.03 criteria. Laboratory data will be summarized by actual value and change from baseline using number of non-missing observations, mean standard deviation, median, minimum and maximum. In addition, shift tables and the incidence of Grade 3 or 4 laboratory values will be presented.

8.3.1.3. Vital Signs

Vital signs will be listed by subject. Values above and below normal ranges will be indicated as will clinical significance. Vital sign data will be summarized by actual value and change from baseline using number of non-missing observations, mean, standard deviation, median, minimum and maximum.

8.3.1.4. Other Safety Data

Data collected for physical examinations, ECGs and related measures will be listed.

8.3.2. *Efficacy Analyses*

8.3.2.1. Primary Efficacy Endpoint

The primary efficacy endpoint is the proportion of subjects treated at the MTD in each disease cohort (AML, MDS or CMML) with objective response (OR) within 3 cycles of study drug (i.e., within 3 months). For subjects with AML, OR is CR, CRi, or PR, as defined above. For subjects with MDS or CMML, OR is CR, PR or marrow CR, as defined above. The proportion of subjects in each disease cohort treated at the MTD will be summarized, and 90% confidence intervals will be estimated.

8.3.2.2. Secondary Efficacy Endpoints

The proportion of MDS subjects with hematologic improvement in the peripheral blood or bone marrow as defined as $\geq 50\%$ reduction in blast count when compared with the baseline value. The 90% confidence interval will be estimated and provided.

Progression-free survival and overall survival curves will be estimated at the MTD by disease cohort using Kaplan-Meier product limit estimates. Median and 90% confidence interval of time-to-event will be estimated. Progression-free survival will be calculated from the date of first dose of study drug to the date of first objective evidence of disease progression or death, whichever is earlier. Overall survival will be calculated from the date of first dose of study drug to the date of death due to any cause. Subjects who did not experience progression or death will be censored at the last follow-up time point.

8.3.3. *Pharmacokinetic Endpoint Analysis*

Mean plasma concentrations of FF-10501 and plasma M1 will be determined at each time point for evaluation of dose-linearity. Because a limited number of plasma concentrations will be determined, full determination of routine pharmacokinetic parameters may not be possible. In addition to mean plasma concentrations, as the data allow, additional pharmacokinetic analyses will be provided (trough levels, $t_{1/2}$, T_{max} , C_{max} , AUC, etc.)

8.3.4. *Pharmacodynamic Endpoint Analysis*

Change from baseline in XMP levels will be measured in blood samples collected from each subject during the study. Correlations between XMP and PK levels of FF-10501 will be made. Pharmacodynamic parameters will be summarized using descriptive statistics

including the number of subjects, mean, standard deviation, minimum, median, maximum, range, and coefficient of variation.

8.3.5. *Other Summaries*

Demographics and concomitant medications, including antibiotic usage, will be summarized using descriptive statistics. Medical history findings and protocol deviations will be listed but not summarized.

9. STUDY MANAGEMENT

9.1. Data Management

The investigator is responsible for completing and maintaining adequate and accurate source documentation. Source documentation constitutes original records, which may include: progress notes, medication administration records, laboratory reports, ECG tracings, discharge summaries, CRF worksheets, etc. Data for this study will be submitted electronically. Access to the database will be provided following a brief on-line training session. Each user will receive a unique username and password, which should not be shared. The investigator must sign the investigator's statement for each subject indicating that the data reported are accurate. See **Appendix E** for Ethical Standards to be followed during the study.

9.2. Monitoring

The Sponsor and Westat are responsible for ensuring the proper conduct of the study with regard to ethics, protocol adherence, site procedures, integrity of the data, and applicable laws and/or regulations. At regular intervals during the study and following completion of the study, the sponsor's study monitors will contact the study site via visits to the site, telephone calls, and letters in order to review study progress, CRF completion, and address any concerns or questions regarding the study conduct. During monitoring visits, the following aspects of study conduct will be carefully reviewed: informed consent of subjects, subject recruitment, subject compliance with the study procedures, source data verification, drug accountability, use of concomitant therapy by subjects, AE and SAE documentation and reporting, and quality of data. Records pertaining to these aspects are expected to be kept current.

9.3. Audits and Inspections

The Sponsor, Westat, a regulatory authority, or an IRB may visit the study site at any time during the study or after completion of the study to perform audits or inspections. The purpose of a sponsor audit or regulatory inspection is to systematically and independently examine all study-related activities and documents to determine whether these activities were conducted according to the protocol, GCP, ICH guidelines, and any other applicable regulatory requirements. Investigators should contact FPHU/Westat immediately if contacted by a regulatory agency about an inspection at their site.

9.4. Amendments

Any amendments to the protocol will be written and approved by the Sponsor. All amendments must be submitted to the IRB for approval prior to implementing the changes. In some instances, an amendment requires changes to the informed consent form, which also must be submitted for IRB approval prior to administration to subjects. If any changes to the CRF are required, Westat will issue supplemental or revised CRF pages on behalf of the sponsor.

